6.10.1. Primary Outcome and Methodology

The primary outcome is the proportion of patients achieving ASAS40 at Week 16 (Visit 8). This is a de-facto (effectiveness) estimand (that is, the effect attributable to the originally randomized treatment, ixekizumab, adalimumab and placebo, at the primary time point of Week 16 in all randomized patients).

The primary outcome related to improvement in symptomatic feature of AxSpA are assessed at Week 16 (Visit 8) prior to adalimumab and placebo patients being rerandomized to ixekizumab during Period 3 (Extended Treatment Period).

The primary analysis will be based on the ITT Population for the Blinded Treatment Dosing Period (Period 2) comparing each ixekizumab treatment group and placebo at Week 16 (Visit 8). The primary analysis is a logistic regression analysis with treatment, geographic region, and baseline CRP status in the model (Section 6.1.1).

In the primary analysis, treatment groups of ixekizumab 80 mg Q2W and Q4W will be analyzed without regard to starting dose. The primary comparison will be tested based on the graphical multiple testing procedures detailed in Section 6.5.

Table RHBV.6.5 provides the detailed analyses including analysis type, method and imputation, population, time point, and treatment comparisons for primary outcome.

6.10.2. Major Secondary Efficacy Analyses

The major secondary outcomes at Week 16 (Visit 8) are:

- Proportion of patients achieving an ASAS20 response
- Change from baseline in ASDAS
- Proportion of patients achieving BASDAI50 response
- Change from baseline in BASFI
- Proportion of patients achieving ASDAS inactive disease
- Change from baseline in MRI SPARCC spine score
- Change from baseline in SF-36 PCS*
- Change from baseline in ASAS-HI*

* Detailed descriptions and analyses on SF-36 PCS and ASAS-HI are described in Table RHBV.6.6 and Table RHBV.6.7.

The major secondary analysis will be based on the ITT Population for Period 2 comparing each ixekizumab treatment group and placebo at Week 16 (Visit 8). In the major secondary analyses, treatment groups of ixekizumab 80 mg Q2W and Q4W will be analyzed without regard to starting dose.

The primary analysis for categorical major secondary outcomes is a logistic regression analysis with treatment, geographic region, and baseline CRP status in the model (Section 6.1.1). Missing data will be imputed using the NRI method (Section 6.3.1).

The primary analysis for continuous major secondary outcomes (except MRI SPARCC spine score) is an MMRM analysis with treatment, geographic region, baseline CRP status, baseline value, visit, baseline value-by-visit, and treatment-by-visit interaction as fixed factors (Section 6.1.1).

The primary analysis for change from baseline in MRI SPARCC spine score is an observed case analysis using ANCOVA with treatment, geographic region, baseline CRP status and baseline value in the model (Section 6.1.1). Only patients with both baseline and Week 16 SPARCC spine score will be included in the analysis.

These major secondary comparisons will be tested based on the graphical multiple testing procedure detailed in Section 6.5.

Table RHBV.6.5 provides the detailed analyses including analysis type, method and imputation, population, time point, and treatment comparisons for major secondary outcomes.

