As a secondary analysis for the primary and major secondary categorical efficacy measures, a categorical mixed-effects model of repeated measures (categorical MMRM) estimating the percentage of patients achieving response across postbaseline visits may be used. The model will include treatment, geographic region, baseline CRP status, visit, treatment-by-visit as fixed factors, as well as the continuous, fixed covariate of baseline value and baseline value-by-visit interaction (when appropriate). The binomial distribution and the logit link will be used. An unstructured covariance matrix will be used to model the within-patient variance-covariance errors. The Kenward-Roger approximation will be used to estimate the denominator degrees of freedom. The Newton-Raphson with ridging optimization technique will be used to aid with convergence. The probability of response, the corresponding 2-sided 95% CI, and the p-value for treatment comparisons at Week 16 (Visit 8) and all other postbaseline visits will be reported.

If the unstructured covariance matrix results in a lack of convergence, the heterogeneous Toeplitz covariance structure, followed by the heterogeneous autoregressive covariance structure, followed by the compound symmetry, will be used. This order is specified according to a decreasing number of covariance parameters in the structure. The sandwich estimator (Diggle et al. 1994) for the covariance estimation will be used by specifying the EMPIRICAL option in SAS PROC MIXED. When sandwich estimation is used, the Kenward-Roger approximation for denominator degrees of freedom cannot be used. Instead, the DDFM=BETWITHIN option will be used to estimate denominator degrees of freedom.

The primary analyses for continuous efficacy and health outcomes variables will be made using MMRM. A secondary analysis for continuous efficacy and health outcomes variables will be made using analysis of covariance (ANCOVA).

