5.3. Determination of Sample Size

Approximately 320 patients will be randomized at a 1:1:1:1 ratio in the Blinded Treatment Dosing Period (Period 2) to ixekizumab 80 mg Q2W, ixekizumab 80 mg Q4W, adalimumab 40 mg Q2W, and placebo. With 80 patients per treatment group, this study will have approximately 96% power to test the superiority of ixekizumab Q2W to placebo for the ASAS40 at Week 16. The following assumptions were used for the power calculations for ASAS40 response rates at Week 16 regardless of starting dose: 44% for ixekizumab 80 mg Q2W treatment group and 16% for the placebo group. A 2-sided Fisher's exact test at the 0.05 level is assumed. These assumptions are based on the review of historical clinical studies in rad-axSpA (etanercept, adalimumab, infliximab, certolizumab, and golimumab [Davis et al. 2003; van der Heijde et al. 2005 and 2006; Inman et al. 2008; Landewé et al. 2014]) and recent secukinumab data in patients who are TNF-naïve (Baeten et al. 2014; Sieper et al. 2014).

6. A Priori Statistical Methods

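### The gated logistic test of ASDAS inactive disease leaves out baseline ASDAS: a valid test, but one that gives up some power

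*SAP*

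**What the plan says.** For the categorical major secondary endpoints, SAP 6.10.2 says that "The primary analysis for categorical major secondary outcomes is a logistic regression analysis". The terms are treatment, geographic region and baseline CRP status, with nonresponder imputation (NRI). SAP 6.10.1 gives the primary endpoint the same model: "The primary analysis is a logistic regression analysis with treatment, geographic region, and baseline CRP status in the model". SAP 6.1.1 adds that region is Europe versus non-Europe, that the test is a Wald test, and that Fisher's exact test is used if sparse data stop the model from producing results. SAP 6.2 defines CRP status by one cut at 5.00 mg/L.

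The continuous endpoints are treated differently. Under SAP 6.10.2 the MMRM for change in ASDAS includes baseline ASDAS and its interaction with visit. SAP 6.2 makes baseline adjustment the general rule for MMRM and ANCOVA. CRP itself is an exception (SAP 6.1.1).

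Table RHBV.6.4 defines ASDAS inactive disease as a score below 1.3. BASDAI50 is an improvement of at least 50% from the patient's own baseline. SAP 6.7.1 lists baseline ASDAS among the variables to be summarised. The legend to Figure RHBV.6.3 places ASDAS inactive disease in Tier 2 of the gated testing scheme.

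**The concern.** Within one section, the same score at the same visit in the same population is adjusted for its baseline when analysed as a change, but not when analysed as a threshold. Neither document gives a reason.

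For a fixed threshold, a patient who starts at a higher ASDAS generally has further to fall. The entry criteria set a minimum for BASDAI and back pain but no ASDAS range, so starting scores can vary widely. If they predict the outcome, leaving them out wastes information.

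At stake is power for a low-rate endpoint in the alpha-controlled scheme, where a missed rejection also means that its alpha is not passed on. The plan states power only for ASAS40, so nothing shows that this endpoint has power to spare.

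**Working it through.** **1. The plan's own figure.** SAP 5.3 states: "With 80 patients per treatment group, this study will have approximately 96% power to test the superiority of ixekizumab Q2W to placebo". The rates are "44% for ixekizumab 80 mg Q2W treatment group and 16% for the placebo group" and "A 2-sided Fisher's exact test at the 0.05 level is assumed". Full enumeration, with a and b the responder counts in the two arms, gives

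power = Σ Bin(a; 80, 0.44) × Bin(b; 80, 0.16) × 1{Fisher p ≤ 0.05} = 96.7%.

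The stated figure reproduces and is not in dispute. It concerns ASAS40 only.

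**2. Simulation for ASDAS inactive disease.** From the documents: four arms of 80; a logistic model with treatment, region and CRP status; a Wald test; NRI; the Fisher fallback; the threshold of 1.3. Assumed:

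- Baseline ASDAS has SD 0.8 and Week 16 ASDAS has SD 1.0, with correlation r. Week 16 = 1.0 × (r × b + √(1 − r²) × e) + arm mean, where b is standardised baseline and e is standard normal.
- A patient responds if Week 16 ASDAS is below 1.3 and the patient has not dropped out. Dropout is 6%, and dropouts count as nonresponders.
- Arm means are set so that the rates, dropout included, are 16% in each active arm and 4% on placebo.
- CRP status has a latent correlation of 0.5 with baseline ASDAS, with 65% elevated. Region is split evenly.

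The model was fitted with and without continuous baseline ASDAS. Both fits keep region and CRP status, so each gain is net of the planned adjustment. Results for Q2W versus placebo at alpha 0.05, 2,500 trials per row:

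| r | Planned model | Plus baseline ASDAS | Gain (points) |
|---|---|---|---|
| 0.3 | 72.5% | 73.7% | 1.2 |
| 0.5 | 71.4% | 76.9% | 5.5 |
| 0.7 | 72.4% | 83.3% | 10.9 |

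The Monte Carlo standard error of one power figure is about √(0.72 × 0.28 / 2500) = 0.9 points. The fallback was used in 3 to 4% of trials.

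**3. Other settings.**

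- Alpha 0.025, 16% versus 4%, no dropout, failed fits left out: 53.4 to 55.4%, 54.9 to 61.0% and 55.7 to 70.4%, which are gains of 2, 6 and 15 points.
- Separate runs at 14% versus 3% with the fallback: gains of about 1, 4 to 5 and 11 points at alpha 0.05, and about 1 to 2, 7 to 8 and 15 to 17 at 0.025. Unadjusted power at 0.025 was about 50 to 53%.
- A further set with NRI dropout and the fallback: about 1 to 2, 3 to 4 and 9 to 11 points at 0.05, and about 1, 6 to 8 and 14 to 16 at 0.025.
- Correlation 0: no gain.

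The fallback matters for the absolute level. At a 3% placebo rate, the chance of no placebo responder is 0.97^80 = 8.7%, and the logistic fit then fails.

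**4. Type I error.** With 10% response in every arm and r = 0.5 (3,000 trials), rejection at alpha 0.05 was 3.3% without and 4.0% with the covariate. There was no inflation.

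**5. The other categorical endpoints.** BASDAI50 depends on Week 16 BASDAI minus half of baseline. With assumed SDs of 1.4 at baseline and 2.2 at Week 16, and ignoring the entry floor, the covariance of standardised baseline with that difference is 2.2 × r − 0.5 × 1.4. This is −0.04, 0.40 and 0.84 at r = 0.3, 0.5 and 0.7, so at low correlation the baseline nearly cancels. At assumed rates of 36% versus 17%, with the floor of 4 applied, the gains were −0.4, 0.8 and 3.9 points. A threshold endpoint at the ASAS40 rates (44% versus 16%) gained 0.5 to 1.6 points, because power was already about 98%.

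**The case against.** The other side has several good points, and most of them stand as limits on the claim.

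- **Validity.** A reader might infer that the planned test is biased or invalid. It is not; omitting a prognostic baseline score costs power only.
- **A dropped covariate.** The protocol's categorical MMRM includes baseline value where appropriate and the SAP's version does not list it, so a reader might infer that the SAP weakened the confirmatory model. It did not. That MMRM is a secondary analysis that may be used. The protocol's logistic model (section 9.2.1) has the same terms as the SAP's.
- **Scope.** A reader might extend the point to every categorical endpoint, the primary included. The calculations do not support this. ASAS20 and ASAS40 combine four domains and have no single baseline score, and BASDAI50 gains almost nothing at low to moderate correlation.
- **Alpha.** SAP 6.5 sends 0.025 per regimen to Tier 1. What reaches Tier 2 depends on earlier rejections and on weights in figures not reproduced in the text available. Treating 0.025 as the level for this endpoint is an assumption.
- **Information already used.** CRP enters the ASDAS formula, and CRP status is in the model. The gains above are net of it, so this reduces the point without removing it. Baseline-adjusted change in ASDAS is itself a gated endpoint, so the evidence on ASDAS does not rest on this test alone.
- **Timing.** SAP section 3 records that Version 2 preceded first unblinding and Version 3 followed it. Changing the gated model in Version 3 would be post hoc. This stands in full.

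**Conclusion.** The point holds for ASDAS inactive disease as a matter of efficiency. For 14 to 16% versus 3 to 4%, 80 per arm, adding baseline ASDAS gains about 1 to 2, 3 to 6 and 9 to 11 points of power at alpha 0.05, and about 1 to 2, 6 to 8 and 14 to 17 at alpha 0.025, for correlations of 0.3, 0.5 and 0.7.

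The rates, SDs, dropout and correlations are assumptions, and the correlation matters most: at 0.3 or below the gain is negligible. The benefit also shrinks when placebo responders are very few, because the Fisher fallback uses no covariate. For BASDAI50 the gain is about 0 to 1 point at correlations of 0.3 to 0.5. No change is claimed for ASAS20 or ASAS40.

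**What to change.** Add baseline ASDAS, as a continuous covariate, to the logistic model for ASDAS inactive disease in SAP 6.10.2. Keep the Fisher fallback. Table RHBV.6.4 sets ASDAS to missing if any component is missing, so state a simple imputation for a missing baseline, such as the mean over all arms, so that every randomised patient stays in the ITT analysis. Report the current model alongside. Baseline BASDAI in the BASDAI50 model is optional.

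The cost is one term in one model and no new data. The odds ratio becomes conditional on baseline ASDAS, and the report should say so.

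As the primary method, this had to be set before the Week 16 unblinding. SAP Version 2, which already revised the region term in the primary model, was the last opportunity. Under Version 3 the gated result must stay with the planned model, and the adjusted model can be added only as a sensitivity analysis labelled as specified after unblinding.

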6.10.3. Additional Analyses of the Primary Outcome

There will be no adjustment for multiple comparisons for additional analyses of the primary outcome, ASAS40.

In the additional analyses of ASAS40, treatment groups of ixekizumab 80 mg Q2W and Q4W will be analyzed without regard to starting dose, unless indicated otherwise.

To support the primary outcome analysis, ASAS40 will be analyzed based on the PPS Population for Period 2 at Week 16 (Visit 8) using a logistic regression analysis with treatment, geographic region, and baseline CRP status in the model (Section 6.1.1). [de-facto estimand]. Missing data will be imputed using the NRI method (Section 6.3.1).

Additional analyses based on the ITT Population for Period 2 for ASAS40, include:

- Comparisons of each ixekizumab treatment group and placebo at postbaseline visits other than Week 16 (Visit 8) using logistic regression analysis with treatment, geographic region, baseline CRP status in the model (Section 6.1.1). [de-facto estimand]. Missing data will be imputed using the NRI method (Section 6.3.1).
- Comparisons of each ixekizumab treatment group and placebo at Week 16 (Visit 8) and all other postbaseline visits using Categorical MMRM analysis with treatment, geographic region, baseline CRP status, visit, treatment-by-visit as fixed factors (Section 6.1.1). [de-jure estimand]
- Comparisons of each ixekizumab treatment group and placebo at Week 16 (Visit 8) and all other postbaseline visits using Fisher's exact test with NRI (Sections 6.1.1 and 6.3.1). [de-facto estimand]

Figures showing the proportion of patients achieving an ASAS40 response at each scheduled visit during Period 2 within each treatment group will be provided.

Time to first ASAS40 response will be assessed based on the ITT Population during Period 2 as described in Section 6.1.1.

Table RHBV.6.5 provides the detailed analyses including analysis type, method and imputation, population, time point, and treatment comparisons for the additional analyses on primary outcome.

6.10.4. Other Secondary Efficacy Analyses

There will be no adjustment for multiple comparisons for other secondary efficacy analyses.

The other secondary efficacy variables for secondary objectives include:

- ASAS40: analyses other than primary analysis (Section 6.10.1) and additional analysis of the primary outcome (Section 6.10.3)
- ASAS20: analyses other than major secondary efficacy analysis (Section 6.10.2)
- ASAS5/6 and partial remission
- ASDAS<2.1: ad hoc analysis post interim 1 database lock
- Change from baseline in individual components of the ASAS criteria (patient global, spinal pain, function [see BASFI below], inflammation [see BASDAI below], CRP [see CRP below], and spinal mobility (lateral spinal flexion) [see BASMI below])
- Change from baseline in BASDAI and inflammation (mean of Q5 and Q6 on BASDAI)
- BASDAI 50: analyses other than major secondary efficacy analysis (Section 6.10.2)
- Change from baseline in ASDAS: analyses other than major secondary efficacy analysis (Section 6.10.2)
- ASDAS inactive disease: analyses other than major secondary efficacy analysis (Section 6.10.2)
- ASDAS disease activity states: inactive disease, low disease activity, high disease activity, very high disease activity; clinically important improvement and major improvement
- Change from baseline in CRP
- Change from baseline in BASFI: analyses other than major secondary efficacy analysis (Section 6.10.2)
- Change from baseline in mobility (BASMI linear and individual components, chest expansion, occiput to wall distance)
- Change from baseline in MRI SPARCC spine score: analyses other than major secondary efficacy analysis (Section 6.10.2)
- Change from baseline in MRI SPARCC SIJ structural score (SSS) for each of the 4 features: fat metaplasia, bone erosion, backfill and ankylosis.
- Change from baseline in MRI ASSpiMRI –Berlin score
- Change from baseline in MRI SPARCC SIJ score
- Change from baseline in enthesitis score (MASES and SPARCC)
- Change from baseline in TJC and SJC scores
- Incidence of peripheral arthritis by TJC and SJC scores of 46/44 joints.
- Incidence rate of anterior uveitis or uveitis flares
- Change from baseline in ASAS-NSAID score (apply to Period 3 analysis only), Section 6.10.4.1.

Treatment comparisons of each ixekizumab treatment group and placebo, as well as adalimumab treatment group and placebo at Week 16 (Visit 8) and all other postbaseline visits during Period 2 will be provided.

The impact of ixekizumab starting doses will be evaluated for the categorical responses (including ASAS40, ASAS20, ASDAS major improvement) and mean change in continuous efficacy measures (including CRP, BASFI) at Week 16 and earlier time point as described in Section 6.1.1.

Descriptive statistics (that is, no inferential testing) will be provided for each treatment group during Period 3, or Combined Periods 2 and 3, as applicable.

Table RHBV.6.5 provides the detailed analyses including analysis type, method and imputation, population, time point, and treatment comparisons for other secondary outcomes.

6.10.4.1. Analyses on NSAID Intake

ASAS-NSAID score is used to present the NSAID (including COX-2 inhibitor) intake by considering the type of NSAID, the total daily dose, and the number of days on which NSAID has been taken during a period of interest (Dougados et al. 2011). Appendix 5 provides the equivalent dose of each NSAID compared to 150 mg diclofenac (Dougados et al. 2011), additional equivalent scores are listed below:

For the NSAID equivalent scoring system, 0 = no intake, 100 = 150 mg diclofenac, 1000 mg naproxen, 200 mg aceclofenac, 400 mg celecoxib, 600 mg etodolac, 90 mg etoricoxib, 200 mg flurbiprofen, 2400 mg ibuprofen, 150 mg indometacin, 200 mg ketoprofen, 15 mg meloxicam, 200 mg nimesulide, 400 mg phenylbutazone, 20 mg piroxicam, 20 mg tenoxicam (Dougados et al. 2011). Additionally, 100 = 180 mg acemetacin, 3600 mg acetylsalicylic acid, 3600 mg salicylic acid, 32 mg lornoxicam, 360 mg loxoprofen, 1000 mg mefenamic acid, 2000 mg nabumetone, 1000 mg niflumic acid, 600 mg tiaprofenic acid, 90 mg pelubiprofen, 240 mg zaltoprofen, 120 mg ketorolac tromethamine (if used intramuscularly [IM] or intravenous [IV]), 40 mg ketorolac tromethamine (if used orally), 120 mg ketorolac (if used intramuscularly [IM] or intravenous [IV]), 40 mg ketorolac (if used orally), 400 mg sulindac, 1200 mg dexibuprofen, 75 mg dexketoprofen, 1110 mg talniflumate. For Vimovo, esomeprazole strontium w/naproxen, esomeprazole w/naproxen and naproxen w/omeprazole, use the score for naproxen; for caffeine with ibuprofen, CAROL-F, and famotidine w/ibuprofen, use the score for ibuprofen; for Dioxaflex Protec and Arthrotec, use the score for diclofenac; for anacin/00141001/, use the score for acetylsalicylic acid; for paynocil, use the score for salicylic acid.

The general formula for calculating ASAS-NSAID score is:

(equivalent NSAID score) x (days of intake during period of interest) x (days per week) / (period of interest in days).

A score is assigned depending on the frequency of NSAID use per week (Dougados et al. 2011):

- 7/7: everyday use
- 6/7: 6 days/week
- 4/7: 4 - 5 days/week

- 2/7: 2-3 days/week
- 0.5/7: ≤1 day/week
- 0: no intake.

Using an example in Dougados et al. 2011, if during a period of interest (between two visits) of 6 months, the patient has taken piroxicam 20 mg during 4 months and if during this 4-month period he has taken piroxicam 3–5 days per week the calculation of ASAS-NSAID is as follows:

$$100 \text{ (20 mg piroxicam score)} \times 120 \text{ (4 months)} \times 4/7 \text{ (3–5 days/ week)} / 180 \text{ (6 months)} = 38.1$$

If the patient has used 10 mg piroxicam during the remaining 2 months on 2 days a week, the NSAID score for this period is:

$$50 \text{ (10 mg piroxicam score)} \times 60 \text{ (2 months)} \times 2/7 \text{ (1–3 days/week)} / 180 \text{ (6 months)} = 4.8$$

In this example, the total score for the 6 month period is 42.9 (38.1 plus 4.8).

ASAS-NSAID score will be summarized for the following endpoints at baseline Week 0 (when applicable) and each scheduled visit of interest, which includes the timeframe after the date of previous visit to the date of current visit:

- Change from baseline in ASAS-NSAID
- Proportion of patients with 50% decrease in ASAS-NSAID scores compared with baseline
- Proportion of patients with ASAS-NSAID score <10
- Proportion of patients with ASAS-NSAID score = 0.

In addition, proportion of patients taking NSAID at specified visit will be summarized.

6.10.5. Sensitivity Analyses

6.10.5.1. pMI

ASAS40, ASAS20, and mean change in ASDAS at Week 16 (Visit 8) will be analyzed based on the ITT Population using the pMI method, as described in Section 6.3.4. Analyses for ASAS40 and ASAS20 will be based on the logistic regression analysis with treatment, geographic region, and baseline CRP status in the model (Section 6.1.1). Analysis for mean change in ASDAS will be based on MMRM analysis. The model will include treatment, geographic region, baseline CRP status, baseline value, visit, baseline value-by-visit, and treatment-by-visit interaction as fixed factors (Section 6.1.1).

